6.10.2.5.3 Listing

All TBUT data will be listed.

6.10.3 Exploratory Endpoints

6.10.3.1 Systemic absorption of nomacopan by blood sampling

Covered under section 6.11.

6.10.3.2 Tear fluid analysis of complement C3, C5 and LTB4

If sufficient data, tear fluid data will be listed.

6.10.3.3 Rescue therapy

The number and percentage of patients that received a rescue medication (as indicated on the Concomitant Medications CRF page) at any stage of the trial (during Day 1 to Day 56 (last dose) and during Day 56 to Day 84 (follow-up visit) to be presented separately) and the number and percentage of patients that were receiving a rescue medication at the end of the trial (indicated as ongoing on the CRF) will be presented in a summary table by treatment group.

The number and percentage of patients that received a rescue medication will be presented for each treatment group for Days 1 to 14, Days 15 to 28, Days 29 to 42 and Days 43 to 56 to compliment the intervals for the efficacy analysis. The percentage will be out of the number of patients at each timepoint who had data for comfort scores to be calculated.

A patient is considered to have taken rescue medication during an interval where the start date (Day 1 or later) occurs during that interval, or if they continue to receive rescue medication that started in a previous interval.

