5.2.3 Exploratory endpoints

- Systemic absorption by blood sampling
- If enough tear fluid can be collected analysis of complement C3, C5 and LTB4 will be performed
- A comparison of the number of patients requiring rescue therapy at any stage of the trial and the number on such therapy at the end of the trial
- Comparison of the Conjunctival impression cytology results in each treatment group from Day 1 to Day 56 using flow cytometry analysis [NB Because these may not be reported for some time after completion of the trial and database lock, they will not form part of the statistical analysis and will be used for research information only]

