Patients should not have used topical ocular steroids for 7 days prior to entry to the trial but, at the discretion of the investigator, may receive them as rescue medication during the trial. A comparison of the number of patients requiring rescue therapy at any stage of the trial and the number on such therapy at the end of the trial will be an additional exploratory endpoint.

Use of systemic immunosuppressives, antihistamines or corticosteroids during the trial is forbidden. Patients who, in the opinion of the investigator, require such treatment will be withdrawn from the trial. If the reason for giving such treatment is related to their primary pathology (AKC, VKC, or severe allergic conjunctivitis (SAC or PAC)) they will be regarded as treatment failures.

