6.8 Rescue Therapy

Topical ocular steroids will be considered Rescue Therapy.

In the event of worsening of signs or symptoms that, in the clinician's opinion is so severe as to necessitate a change of medication, ciclosporin and/or antihistamines may be introduced or increased in dose/frequency and this will be considered as a treatment failure for purposes of efficacy analysis.

The introduction or increase in dose/frequency of ciclosporin or antihistamines will be considered as Rescue Therapy.

After entry into the trial, subjects will be recommended to not receive Rescue Therapy from the first dose of rVA576 as far as possible unless assessed by PI as needed.

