7.2 Withdrawal Criteria

In accordance with applicable regulations, a patient has the right to withdraw from the study at any time and for any reason without prejudice to their future medical care by the physician or at the Institution. Should a patient withdraw from the study, the patient will not undergo any further study-specific procedures or receive any treatment mandated by the protocol.

If a patient fails to attend scheduled trial assessments, the Investigator must determine the reasons and the circumstances as completely and accurately as possible.

In the event of the premature withdrawal of a patient from the trial, the end of trial visit should be carried out as completely as possible. Minimally, a safety assessment should be performed.

In the case of withdrawal due to the occurrence of unacceptable toxicity, the patient will be requested to remain under the supervision of the Investigator until the toxicity has resolved or is no longer considered to be clinically significant by the Investigator.

If an AE classified as severe results in patient withdrawal from the study, the patient will be followed until the AE (or SAE) resolves or stabilises, and any interventions required to resolve or stabilise the event will be recorded in the eCRF.

All withdrawals must be documented in the eCRF. A patient may be withdrawn in any of the following circumstances:

- Withdrawal of consent (mandatory withdrawal)
- Intake of non-permitted concomitant medications (may be discussed with the Sponsor and dependent on the nature of the medication)
- Patient is non-compliant with more than three consecutive missed doses and two missed clinic visits, in the opinion of the Investigator (discretionary withdrawal)
- If discontinuation is considered necessary by the Investigator and/or Sponsor (mandatory withdrawal)
- Request of Regulatory Agency (mandatory withdrawal)
- Patient develops an illness that would compromise his participation in the study (may be discussed with sponsor)
- Pregnancy

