6.10.2.3.2 Analysis

Change from baseline (Day 1) for the total score at Day 14, Day 28, Day 42 and Day 56 will be analysed using a mixed-effect model for repeated measures. The model will include baseline total clinical score as a covariate, treatment group, visit and patient group (AKC/VKC or SAC/PAC) as fixed factors and the treatment arm by visit interaction.

The variance/covariance matrix structure that results in best model fit will be selected using the process described in section 6.10.2.1.2.

Assumptions of normality will be assessed visually using diagnostic plots. Should assumptions of normality not hold, transformations such as percentage change and ratio to baseline will be considered. If there remains uncertainty regarding the assumptions an alternative analysis, for example non-parametric analysis, may be considered.

The LS means and 95% confidence interval will be presented for each visit and treatment. The adjusted LS mean difference (nomacopan - placebo) and 95% confidence interval will be presented for each visit.

A null hypothesis of no change in clinical score at Day 56 between treatment groups (nomacopan - placebo) will be assessed and a p-value will also be reported based on the relevant mixed-effect model.

Where there is sufficient data (see section 6.2) the item scores will be analysed using the same method as for the total score.

Where there is a sufficient number of patients receiving rescue therapy, additional analysis (as described above) may be conducted using the same methods as the recorded clinical scores by imputing the worst-case score for all post-rescue therapy visits.

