6.17 Changes from the Protocol Planned Analysis

- Section 11.1 of the protocol states that the baseline value will be defined as the pre-dose value on Day 1, if that is missing, it will be defined from the most recent value available. This has been updated to take account of any patients who do not take their first dose on Day 1.
- Section 11.3 of the protocol states that the weekly comfort scores for postinstillation comfort, as graded on patient diary cards will be compared. To be in-line with the secondary endpoint, the scores over the two-weekly period will be compared.
- Section 11.8 of the protocol states that the Safety Analysis Set will include only randomized subjects from Part 2 of the study. To be in line with ICH E9 guidelines section 6.3 we will include all treated subjects regardless of the part of the study they are enrolled into.

7 **REFERENCES**

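### Withdrawal for systemic treatment of the eye disease is a treatment failure in the protocol, but it does not trigger the SAP's optional worst-case score analysis and is not counted beside rescue (minor)

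*SAP*

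**What the plan says.** **Protocol.** Section 6.3 bans systemic immunosuppressives, antihistamines and corticosteroids during the trial and withdraws patients who need them. If the reason is the eye disease, "they will be regarded as treatment failures". Sections 6.3 and 6.8 also class a topical step-up for severe worsening as a treatment failure, there explicitly for the efficacy analysis. Section 6.8 defines rescue as topical ocular steroids, and adds: "The introduction or increase in dose/frequency of ciclosporin or antihistamines will be considered as Rescue Therapy". Systemic corticosteroids and non-ciclosporin immunosuppressives are not named as rescue. The exploratory endpoint in section 5.2.3 concerns rescue only: "A comparison of the number of patients requiring rescue therapy at any stage of the trial". After withdrawal, under section 7.2, "the patient will not undergo any further study-specific procedures", although "the end of trial visit should be carried out as completely as possible".

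**SAP.** Section 6.10.3.3 reports "The number and percentage of patients that received a rescue medication (as indicated on the Concomitant Medications CRF page) at any stage of the trial". Section 6.10.2.3.2 allows, if enough patients receive rescue, an additional analysis of the clinical score "by imputing the worst-case score for all post-rescue therapy visits". Section 6.2 otherwise rules out imputation. No SAP section defines or uses a treatment-failure status.

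**The concern.** The protocol treats two events as failure: a topical step-up for worsening, and withdrawal because the eye disease needs systemic treatment. The SAP's only failure-like handling responds to the first. If the worst-case analysis is run, the order of severity can be reversed. A patient given extra ciclosporin drops has the worst score carried into every later visit. A patient whose disease was bad enough for a systemic corticosteroid contributes only the scores recorded before withdrawal.

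That analysis presumably exists to stop treatment from outside the trial hiding a poor outcome. Leaving out the more severe failure weakens it in whichever arm the failure occurs. The same patient is also absent from the rescue numerator, and no nearby row shows that a failure of another kind took place.

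**Working it through.** The plan states no failure rate, power or effect size, so there is no figure to reproduce. The check sets the rules side by side and then sizes one patient.

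**Step 1. Two patients under the rules as written, if the worst-case analysis is run**

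| | A: ciclosporin drops increased | B: directly to a systemic corticosteroid, withdrawn, no rescue flag |
|---|---|---|
| Protocol status | Failure (6.3, 6.8) | Failure if due to the eye disease (6.3) |
| Rescue under protocol 6.8 | Yes | Not named |
| SAP 6.10.3.3 numerator | Counted | Not counted |
| SAP 6.10.2.3.2 worst-case score | Imputed at all later visits | Not imputed |
| Later visits in that analysis | Worst-case score | Missing (SAP 6.2) |

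Column B is limited to these drug classes because protocol 6.8 does not say topical when it names ciclosporin and antihistamines. Systemic use of those two could be read as rescue.

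**Step 2. One patient in the any-stage rate**

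Inputs: up to 16 patients randomised 1:1 in Part 2 (protocol 6.7 and 11.4, SAP 3 and 4), so 16/2 = 8 per arm if recruitment is full. The denominator appears to be all patients in the arm (SAP 6.8 read with 6.1).

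- 8 per arm: 1/8 = 12.5 percentage points
- 7 per arm: 1/7 = 14.3
- 6 per arm: 1/6 = 16.7

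Assumed example with 8 in the arm: 2 patients have topical rescue and 1 goes directly to a systemic corticosteroid. The rescue row shows 2/8 = 25.0%. A row counting either event would show 3/8 = 37.5%.

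**Step 3. Clinical scores for that patient**

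Assume withdrawal on Day 20. The planned post-baseline scores are at Days 14, 28, 42 and 56. Day 14 stays in the model. Days 28, 42 and 56 are missing, which is 3 of 4. An end-of-trial assessment may exist, but SAP 6.4 tabulates scheduled assessments only and does not say how an early final visit is assigned. If it were assigned to Day 28, 2 of 4 would be missing.

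**Step 4. What imputing one patient could do to an arm mean**

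The SAP does not define the worst-case score. Assume it is the scale maximum, that the patient entered at the minimum qualifying score, and that the comparison is with no change. This is a raw mean over 8 patients, not the model estimate.

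- AKC/VKC: (33 − 18)/8 = 15/8 = 1.9 points
- SAC/PAC: (27 − 15)/8 = 12/8 = 1.5 points

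These are upper values under those assumptions. The shift falls towards 0 as the entry score approaches the maximum.

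**The case against.** **No planned analysis was dropped.** A reader might infer that the SAP removed a failure analysis and left this out of section 6.17, "Changes from the Protocol Planned Analysis". The documents do not support that. Protocol 5.2 lists no failure endpoint and protocol 11 plans no failure analysis. The explicit link to efficacy analysis is attached to topical escalation, not to the sentence on systemic treatment. The three items in SAP 6.17 therefore conceal nothing. Nor is the rescue-only count an error, since it reports the endpoint that protocol 5.2.3 describes. This objection stands in full.

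**The event is not lost.** Protocol 8.2.2 requires worsening of a pre-existing condition to be recorded as an adverse event. If coded to Eye disorders, it counts in the primary endpoint (SAP 6.14.1.1). Withdrawal reasons are tabulated (SAP 6.5), concomitant medications are tabulated and listed (SAP 6.8), and key efficacy results are listed by patient (SAP 6.10.4). With at most 16 randomised patients, individual cases can be traced. This largely stands. Two limits remain. A patient who simply fails to improve may generate no adverse event. The withdrawal circumstances in protocol 7.2 also include no item for lack of efficacy, so the recorded reason may not identify disease failure.

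**The path is narrow.** The patient must skip the topical steps, receive a systemic drug outside the rescue definition, and not be flagged as rescue on a CRF page that the documents do not show. A site could flag the drug, and the gap would then close. This stands, and it is why the point is conditional.

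**The remedy is a composite that the protocol does not list.** This also stands. It is why the rescue rows should stay unchanged and the added row be descriptive only.

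None of these objections explains why, if the worst-case analysis is run, the milder failure should be penalised and the more severe one left missing.

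**Conclusion.** The inconsistency is real and minor. Protocol 6.3 gives systemic-treatment withdrawal for the eye disease a failure status that the SAP does not use, and the trigger in SAP 6.10.2.3.2 can treat a milder failure more harshly than a more severe one. The size is 12.5 percentage points of an arm's rate per patient with 8 per arm. If the worst-case analysis is run, one imputed patient moves the arm mean by up to 1.9 points (AKC/VKC) or 1.5 points (SAC/PAC) on the assumptions shown.

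The conclusion rests on three conditions: the patient has no earlier topical rescue, the systemic drug is not flagged as rescue, and the optional analysis is carried out. The last condition applies to the score part only. No rate for this path is documented. A reader might infer that the trial's main result is biased, but the primary endpoint does not use rescue or failure status and can itself capture the worsening. The affected outputs are an exploratory table and an optional supplementary analysis of a secondary endpoint.

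**What to change.** **SAP 6.10.2.3.2.** Make the trigger rescue therapy, or withdrawal for systemic treatment of the eye disease as described in protocol 6.3. Impute the worst-case score at scheduled visits after either event.

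**SAP 6.10.3.3.** Keep the rescue rows as they are. Add one descriptive any-stage row for Day 1 to Day 56 counting patients with either event, over all FAS patients in the arm. Show the number withdrawn for other reasons beside it, because those patients count as non-failures in the row.

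**Identification.** Use withdrawal reasons and concomitant medications. If the CRF does not separate systemic treatment of the eye disease from other reasons, decide by masked review before unmasking.

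**Cost.** SAP text, one programmed flag, one table row and, if needed, a masked review of the withdrawn patients (at most 16 in Part 2). No new visits, patients or data are required. The downside is that the new row is a composite outside the protocol's list of endpoints, so it should be labelled as such and read beside the rescue rows, not in place of them.

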6.2 General Derivations

This section provides details of general derivations. Detailed descriptions of specific parameter derivations are provided later in the SAP.

• Definition of baseline

The Baseline value will be defined as the pre-dose value on Day 1, if that is missing or the first administration is not on Day 1, it will be defined from the most recent value available and recorded prior to the first administration of study treatment.

Incomplete dates

For calculation purposes, incomplete dates will be completed using worst case, the most conservative value possible. For example, if the start date has a missing day value, the first day of the month will be imputed for study day computations. If day is

missing for an end date, the last day of the month will be imputed. Similar logic will be assumed for missing month and year components.

• Methods for handling withdrawals and missing data

There will be no imputation of missing data. Screening data will be used if baseline is missing.

Statistical testing and graphical presentations will not be carried out for any given score or measurement if there are less than 5 results, for either the placebo or active group, for that score or measurement at any single time point.

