6.10.2 Secondary Endpoints

6.10.2.1 Post-instillation comfort

Post-instillation comfort scores will only be available for the least comfortable eye. The eye that the scoring was recorded on will not be captured on the eCRF.

A score of 0 to 4 will be recorded at 0.5 min, 1 min, 2 min, 3 min and 5 min each morning and evening on diary card.

The total score over two-week periods for days 1 to 14, 15 to 28, 29 to 42 and 43 to 56 will be calculated for each patient by summing the scores from the five timepoints taken each morning and evening over the 14 days, therefore the total score will have a possible range of 0 to 560. If there are 20 or more missing data points during the period, then the total score will not be calculated and set to missing.

For derived non-missing scores, an average score for the period will also be calculated as follows:

$$Average \ score = \frac{Total \ score}{Number \ of \ non - missing \ days}$$

The average score at each two week-period will be classified as follows: an average total comfort score of < 10 will be deemed to be comfortable/acceptable, 10 - 19 will be moderately uncomfortable, 20 - 29 will be very uncomfortable and ≥ 30 will be severely/unacceptably uncomfortable.

The number and percentage of missing data over the two-week period will be calculated, where 140 data points would expected to be recorded over 14 day period.

Should the five scores not be available at any morning or evening timepoint there will be no imputation, and the total score and classification will be derived for the two-week period for that patient regardless of missing data.

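### The two-week rescue table in SAP 6.10.3.3 divides by patients with comfort-diary data, so its percentages are inflated when an arm with a rescue has a patient without such data

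*SAP*

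**What the plan says.** SAP 6.10.3.3 plans two rescue displays.

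- **Any-stage and end-of-trial.** This counts patients who "received a rescue medication (as indicated on the Concomitant Medications CRF page) at any stage of the trial", and those still on rescue at the end. No comfort-based denominator is attached. It answers the exploratory endpoint in Protocol 5.2.3: "A comparison of the number of patients requiring rescue therapy at any stage of the trial", together with the number on rescue at the end.
- **By two-week interval.** "The number and percentage of patients that received a rescue medication will be presented for each treatment group for Days 1 to 14", and likewise for the three later intervals. For this table, "The percentage will be out of the number of patients at each timepoint who had data for comfort scores to be calculated". On timing, "A patient is considered to have taken rescue medication during an interval where the start date (Day 1 or later) occurs during that interval"; rescue that began in an earlier interval and is still running also counts.

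Who has comfort data is settled in SAP 6.10.2.1: "If there are 20 or more missing data points during the period, then the total score will not be calculated and set to missing". The same section closes by saying that the total is derived however much is missing, and SAP 6.10.2.1.1 counts patients with some data.

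Two other sections bear on the denominator. SAP 6.1 bases concomitant-medication percentages on the analysis set. SAP 6.8 says that rescue is shown in the same manner as concomitant medication, with a pointer to 6.10.3.3.

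On dates, SAP 6.2 gives this example: "if the start date has a missing day value, the first day of the month will be imputed for study day computations". Protocol 6.8 defines rescue broadly: besides topical ocular steroids, "The introduction or increase in dose/frequency of ciclosporin or antihistamines will be considered as Rescue Therapy".

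**The concern.** Numerator and denominator come from different sources. Rescue is read from a medication page that is completed whether or not the diary is kept. The denominator is read from diary scores recorded after each drop. A patient who worsens, starts rescue and then stops the drops or the diary can leave the denominator and stay in the numerator, and ongoing rescue carries that patient into later intervals. The ratio is then not a proportion of any defined group.

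At stake is the readability of a descriptive table meant to sit beside the efficacy intervals. With about 8 patients per arm, one or two missing diaries move the percentage noticeably. If diaries are completed differently in the two arms, the arms would appear to differ in rescue use for that reason alone.

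**Working it through.** **Inputs.** Up to 16 patients in Part 2 (SAP 3), randomised 1:1 (SAP 4), so 16 / 2 = 8 per arm. Five comfort scores per dose, each 0 to 4, twice a day for 14 days (SAP 6.10.2.1).

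**The plan's own figures.** 5 × 2 × 14 = 140 points per interval, and 140 × 4 = 560 for the maximum total. Both agree with the SAP. The 20-point limit is 20 / 140 = 14.3%, or 20 / 10 = 2 full diary days.

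**Rate as written.** Let r be the patients rescued in the interval, k those with comfort data, and n = 8. The SAP gives r / k; the arm's rate is r / n. They agree only when k = n or r = 0. The SAP figure passes 100% whenever r > k.

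| r | k | SAP rule r / k | Arm rate r / 8 |
|---|---|---|---|
| 4 | 8 | 50% | 50% |
| 2 | 6 | 33.3% | 25% |
| 4 | 5 | 80% | 50% |
| 5 | 4 | 125% | 62.5% |

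**Effect of the two missing-data rules.** Suppose 4 of 8 are rescued and 3 patients each miss 4 diary days, which is 4 × 10 = 40 points. Under the 20-point rule those 3 have no total, k = 5, and the table shows 80%. Under the rule that derives the total regardless, they keep a total, k = 8, and it shows 50%.

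**Illustration under assumed rates.** The documents give no rescue or diary-completion rates, so these are assumptions. Draw r from a binomial with n = 8, and draw who has comfort data separately among rescued and non-rescued patients. The mean is over cases with k > 0; the chance of r > k includes k = 0.

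| True rescue rate | Comfort data: rescued / others | Mean reported rate | Chance that r > k |
|---|---|---|---|
| 25% | 80% / 80% | 32.5% | 0.4% |
| 25% | 50% / 90% | 34.3% | 1.3% |
| 50% | 80% / 80% | 65.0% | 5.6% |
| 50% | 50% / 90% | 80.1% | 18.2% |
| Any | 100% / 100% | true rate | 0% |

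Inflation appears even when missing diaries are unrelated to rescue, because the numerator keeps patients whom the denominator drops.

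**Dates, separately.** Let Day 1 be 10 March, with rescue starting on 20 March: 20 − 10 + 1 = Day 11. Recorded only as March, it is imputed to 1 March, 9 days before Day 1. It fails the condition that the start be on Day 1 or later, and it did not start in a previous interval, so no interval counts it. The SAP 6.8 rule that treats unclear medications as concomitant does not place it in one. Recorded only as April, it would be imputed to 1 April, which is Day 23, and counted in Days 15 to 28. The loss is thus confined to the entry month, and does not occur if Day 1 is the 1st.

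**The case against.** The strongest reply is that the table is supplementary, exploratory and untested. The protocol's endpoint is met by the any-stage and end-of-trial figures, which this denominator does not touch. Counts are printed beside percentages, SAP 6.10.2.1.1 summarises missing diary points by interval, and the data are listed, so an attentive reader could see a mismatch. All of this stands, and it keeps the point minor.

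It can also be said that the intent was to restrict both counts to patients with comfort data, and that the table shells, which are a separate document, may show this. That is possible, but the text does not say so, and it would not fully cure the problem. If 4 of 8 are rescued and the 3 without a score are all among them, the restricted rate is 1 / 5 = 20% against 50%. The appeal to SAP 6.8 is also less than conclusive, because that section points back to 6.10.3.3.

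A reader might infer more than the documents support:

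- **That the interval percentages are wrong in any event.** They are right if all patients have comfort data.
- **That this is the trial's only count of treatment failure.** Protocol 6.3 also treats disease-related need for systemic treatment as failure, and SAP 6.5 summarises withdrawal reasons.
- **That lost dates help push rates above 100%.** They lower the numerator and act the other way.
- **That dose increases of background drugs are lost.** This happens only if the CRF keeps the drug's original start date, and the CRF conventions are not shown.
- **That a known share of rescues is dropped.** Any share would need the number of partial dates and the spread of entry and rescue dates. None is given.

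The absence of a named confidence interval for rescue is a different matter from this defect.

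**Conclusion.** The point holds for the interval table only. As written, its percentage is too high whenever an arm with at least one rescue has a patient without comfort data, and it can exceed 100%. With 8 per arm the error runs from nothing to, for example, 80% in place of 50%. Its actual size depends on diary completeness, which is unknown, and on which rule in SAP 6.10.2.1 is applied. The interval denominator also departs from the analysis-set basis in SAP 6.1, which SAP 6.8 appears to extend to rescue.

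The missing-day problem is real but secondary. It follows from reading SAP 6.2 and 6.10.3.3 together, and its frequency cannot be determined. Neither problem affects the primary endpoint or any planned test.

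**What to change.** In SAP 6.10.3.3:

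1. Make the interval denominator the Full Analysis Set patients in the arm, or those still in the trial at the start of the interval. State that the numerator is a subset of it, and print n/N. This follows the analysis-set approach of SAP 6.1 and 6.8.
2. For a rescue flagged on the CRF with a missing start day in the month of Day 1, impute the later of the 1st of the month and Day 1. In the example above that is 10 March, so the rescue is counted in Days 1 to 14.
3. State that, for this table, a rescue consisting of a dose or frequency increase is dated at the increase.

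The two rules in SAP 6.10.2.1 should be reconciled for the comfort analysis, but with the first change the rescue table no longer depends on them. The cost is a few sentences of SAP text and minor programming, with no new data unless the CRF does not record the date of an increase.
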